6.12. Health Outcomes and Quality of Life Analyses

The health outcomes and quality of life (QoL) measures are Itch NRS, DLQI, Skin Pain VAS, Patient's Global Assessment of Disease Severity (PatGA), Patient's Assessment of Pain VAS, and Patient's Global Assessment of Disease Activity VAS.

The health outcomes and QoL analyses will be conducted on the Blinded Treatment Periods. There will be no adjustment for multiple comparisons.

[Table RHCR.6.6](#) include the description and derivation of the health outcomes and QoL measures. [Table RHCR.6.7](#) provides the detailed analyses including analysis type, method and imputation, population, time point, and treatment group comparisons for health outcomes and QoL analyses.

Table RHCR.6.6. Description and Derivation of Health Outcomes and Quality-of-Life Measures

Measure	Description	Variable	Derivation / Comment	Handling of Missing Components
Itch NRS	Itch Numeric Rating Scale (NRS): is a single-item, patient-reported outcome (PRO) measure designed to capture information on the overall severity of a patient’s itching due to their psoriatic skin condition by having the patient circle the integer that best describes the worst level of itching in the past 24 hours on an 11-point NRS anchored at 0 representing “no itching” and 10 representing “worst itch imaginable.”	Itch NRS score	Range from 0 to 10.	Single item, missing if missing
		Itch NRS score change from baseline	Calculated as: observed Itch NRS – baseline Itch NRS	Missing if baseline or observed value is missing
		Itch NRS ≥ 4 improvement from baseline	Reduced/decreased of ≥ 4 point from baseline	Missing if baseline or observed value is missing
		Itch NRS = 0	Defined as a post-baseline Itch NRS score of 0	Missing if Itch NRS score is missing
DLQI	Dermatology Life Quality Index (DLQI): is a validated, dermatology-specific, patient-reported measure that evaluates patient’s health-related quality of life. This questionnaire has 10 items that are grouped in 6 domains, including symptoms and feelings, daily activities, leisure, work and school, personal relationships, and treatment. The recall	DLQI symptoms and feelings domain	Sum of responses of questions #1 and #2: #1. How itchy, sore, painful or stinging has your skin been? #2. How embarrassed or self-conscious have you been because of your skin?	If one question in a domain is missing, that domain is missing.
		DLQI daily activities domain	Sum of responses of questions #3 and #4: #3. How much has your skin interfered with you going shopping or looking after your home or garden? #4. How much has your skin influenced the clothes you wear?	If one question in a domain is missing, that domain is missing.
		DLQI leisure domain	Sum of responses of questions #5 and #6: #5. How much has your skin affected any social or leisure activities? #6. How much has your skin make it difficult for you to do any sport?	If one question in a domain is missing, that domain is missing.
		DLQI work and school	Sum of responses of questions question #7A and #7B:	If the answer to question

Measure	Description	Variable	Derivation / Comment	Handling of Missing Components
	period of this scale is over the “last week”. Response categories and corresponding scores are: Very much = 3 A lot = 2 A little = 1 Not at all = 0 Not relevant = 0	domain	#7A. Has your skin prevented you from working or studying? #7B. If No: how much has your skin been a problem at work or studying?	#7A is missing, this domain is missing. If #7A is No, and #7B is missing, this domain is missing.
		DLQI personal relationships domain	Sum of responses of questions #8 and #9: #8. How much has your skin created problems with your partner or any of your close friends or relatives? #9. How much has your skin caused any sexual difficulties?	If one question in a domain is missing, that domain is missing.
		DLQI treatment	Response of question #10: #10. How much of a problem has the treatment for your skin been, for example by making your home messy, or by taking up time?	If one question in a domain is missing, that domain is missing.
		DLQI total score	A DLQI total score is calculated by summing all 10 question responses, and has a range of 0 to 30 (less to more impairment) (Finlay and Khan 1994; Basra et al. 2008).	If two or more questions are missing, the total score is missing. Note: #7B could be a valid missing while #7A is not “No.” That is, #7 should be considered as one question.
		DLQI (0,1)	A DLQI (0,1) response is defined as a post-baseline DLQI total score of 0 or 1. A DLQI total score of 0 to 1 is considered as having no effect on a patient’s HRQoL (Khilji et al. 2002; Hongbo et al. 2005).	Missing if DLQI total score is missing
		DLQI (0)	A DLQI (0) response is defined as a post-baseline DLQI total score of 0.	Missing if DLQI total score is missing
		DLQI total score \geq 5 improvement from baseline	Reduction/decrease of \geq 5 points from baseline. A 5-point change from baseline is considered as the minimal clinically important difference threshold.	Missing if baseline or observed value is missing
		DLQI total score and domain scores change from baseline	Calculated as: observed DLQI (total score or domain scores) – baseline DLQI (total score or domain scores)	Missing if baseline or observed value is missing

Measure	Description	Variable	Derivation / Comment	Handling of Missing Components
Skin pain VAS	Skin Pain Visual Analog Scale (VAS): is a patient-administered scale designed to measure skin pain from psoriasis using a 100-mm horizontal VAS. Overall severity of a patient’s skin pain from psoriasis at the present time is indicated by placing a single mark on the horizontal scale (0 = no skin pain; 100 = severe skin pain).	Skin Pain VAS	Range from 0 (no skin pain) to 100 (severe skin pain). Note: higher value indicates greater severity of illness.	Single item, missing if missing
		Skin Pain VAS change from baseline	Calculated as: observed skin pain VAS – baseline skin pain VAS	Missing if baseline or observed value is missing
		Skin Pain VAS = 0	Defined as a post-baseline Skin Pain VAS score of 0	Missing if observed value is missing
Patient’s Global Assessment of Disease Severity (PatGA)	Patient’s Global Assessment of Disease Severity (PatGA) is a patient-administered, single-item scale assessing a number on a 0 to 5 on a NRS.	PatGA score	Severity of the patient’s psoriasis “today” from 0 (clear; no psoriasis) to 5 (severe)	Single item, missing if missing
		PatGA(0,1)	Defined as a post-baseline PatGA score of 0 or 1	Missing if observed value is missing
		PatGA (0)	Defined as a post-baseline PatGA score of 0	Missing if observed value is missing
Patient’s Assessment of Pain VAS	Patient’s Assessment of Pain Visual Analog Scale (VAS): is a patient-administered scale designed to measure joint pain using a 100-mm horizontal VAS. Overall severity of a patient’s joint pain at the present time is indicated by placing a single mark on the horizontal scale (0 = no	Patient’s assessment of pain VAS	Range from 0 (no joint pain) to 100 (severe joint pain). Note: higher value indicates greater severity of illness.	Single item, missing if missing
		Patient’s assessment of pain VAS change from baseline	Calculated as: observed Patients Assessment of Pain VAS – baseline Patients Assessment of Pain VAS	Missing if baseline or observed value is missing
		Patient’s assessment of pain VAS percent improvement from baseline	Calculated as: $Percent\ improvement\ from\ baseline = 100 \times \frac{Baseline - Observed}{Baseline}$ If a patient has experienced an improvement, this measure will be positive. If a patient has experienced a worsening in the condition, this measure will be negative.	Missing if baseline or observed value is missing

Measure	Description	Variable	Derivation / Comment	Handling of Missing Components
	joint pain; 100 = severe joint pain).			
Patient Global Assessment of Disease Activity Visual Analog Scale (VAS)	Patient’s Global Assessment of Disease Activity Visual Analog Scale (VAS): is a patient-administered scale designed to measure overall disease activity of psoriatic arthritis using a 100-mm horizontal VAS. Overall severity of a patient’s joint pain at the present time is indicated by placing a single mark on the horizontal scale (0 = no arthritis activity; 100 = extremely active arthritis).	Patient global assessment of disease activity VAS	Range from 0 (no disease activity) to 100 (severe disease activity). Note: higher value indicates greater severity of illness.	Single item, missing if missing
		Patient global assessment of disease activity VAS change from baseline	Calculated as: observed Patient Global Assessment of Disease Activity VAS – baseline Patient Global Assessment of Disease Activity VAS	Missing if baseline or observed value is missing
		Patient global assessment of disease activity VAS percent improvement from baseline	Calculated as: $Percent\ improvement\ from\ baseline = 100 \times \frac{Baseline - Observed}{Baseline}$ If a patient has experienced an improvement, this measure will be positive. If a patient has experienced a worsening in the condition, this measure will be negative.	Missing if baseline or observed value is missing

Table RHCR.6.7. Description of Health Outcomes and Quality-of-Life Analyses

Measure	Variable	Analysis Method (Sections 6.1.3 and 6.3)	Analysis Population (Section 6.1.1)	Comparison / Time Point	Analysis Type
Itch NRS	Itch NRS change from baseline	MMRM; ANCOVA with mBOCF for the Blinded Treatment Periods	ITT Population	IXE vs. GUS at all post-baseline visits	Exploratory analysis (Section 6.11.3).
	Itch NRS ≥ 4 improvement from baseline	CMH test with NRI; Fisher’s Exact test with NRI	ITT Population - with baseline Itch NRS Score ≥ 4	IXE vs. GUS at all post-baseline visits	Exploratory analysis (Section 6.11.3).
	Itch NRS = 0	CMH test with NRI; Fisher’s Exact test with NRI	ITT Population - with Baseline Itch NRS Score > 0	IXE vs. GUS at all post-baseline visits	Exploratory analysis (Section 6.11.3).
DLQI	DLQI total score and domain scores change from baseline	MMRM; ANCOVA with mBOCF for the Blinded Treatment Periods	ITT Population	IXE vs. GUS at all post-baseline visits	Exploratory analysis (Section 6.11.3).
	DLQI ≥ 5 improvement from baseline	CMH test with NRI; Fisher’s Exact test with NRI	ITT Population with Baseline DLQI ≥ 5	IXE vs. GUS at all post-baseline visits	Exploratory analysis (Section 6.11.3).
	DLQI (0, 1)	CMH test with NRI; Fisher’s Exact test with NRI	ITT Population	IXE vs. GUS at all post-baseline visits	Exploratory analysis (Section 6.11.3).
Skin Pain VAS	Skin Pain VAS change from baseline	MMRM; ANCOVA with mBOCF for the Blinded Treatment Periods	ITT Population	IXE vs. GUS at all post-baseline visits	Exploratory analysis (Section 6.11.3).
	Skin Pain VAS = 0	CMH test with NRI; Fisher’s Exact test with NRI	ITT Population – with baseline Skin Pain VAS > 0	IXE vs. GUS at all post-baseline visits	Exploratory analysis (Section 6.11.3).
Patient’s Global Assessment of Disease Severity (PatGA)	PatGA (0)	CMH test with NRI; Fisher’s Exact test with NRI	ITT Population	IXE vs. GUS at all post-baseline visits	Exploratory analysis (Section 6.11.3).
	PatGA (0, 1)	CMH test with NRI; Fisher’s Exact test with NRI	ITT Population	IXE vs. GUS at all post-baseline visits	Exploratory analysis (Section 6.11.3).
	PatGA ≥ 2 improvement from baseline	CMH test with NRI; Fisher’s Exact test with NRI	ITT Population with Baseline PatGA ≥ 2	IXE vs. GUS at all post-baseline visits	Exploratory analysis (Section 6.11.3).

Measure	Variable	Analysis Method (Sections 6.1.3 and 6.3)	Analysis Population (Section 6.1.1)	Comparison / Time Point	Analysis Type
Patient's Assessment of Pain VAS	Patient's Pain VAS change from baseline; percent improvement	ANCOVA with mBOCF; MMRM for the Blinded Treatment Periods	ITT Population – with psoriatic arthritis at baseline	IXE vs. GUS at all post-baseline visits	Exploratory analysis (Section 6.11.3).
Patient Global Assessment of Disease Activity VAS	Patient's global assessment VAS change from baseline; percent improvement	ANCOVA with mBOCF; MMRM for the Blinded Treatment Periods	ITT Population – with psoriatic arthritis at baseline	IXE vs. GUS at all post-baseline visits	Exploratory analysis (Section 6.11.3).

Abbreviations: ANCOVA = Analysis of Covariance; CMH = Cochran-Mantel-Haenszel; DLQI = Dermatology Life Quality Index; GUS = Guselkumab 100 mg; ITT = Intent-to-Treat; IXE = Ixekizumab 80 mg; mBOCF = modified baseline observation carried forward; MMRM = Mixed-effects Model of Repeated Measures; NRI = Nonresponder Imputation; NRS = Numeric Rating Scale; PatGA = Patient Global Assessment of Disease Severity ;VAS = Visual Analogue Scale.

6.12.1. Exploratory Health Outcome and Quality of Life Analyses – Optimal Psoriasis Assessment Tool (OPAT) Validation

Exploratory Health Outcome and Quality of Life Analyses – Optimal Psoriasis Assessment Tool (OPAT) Validation PASI, as a complex index to measure psoriasis severity, is time-consuming to complete, and it is known that this is not regularly collected by physicians for their psoriasis patients. Development of a real-world useful tool (e.g., Optimal Psoriasis Assessment Tool [OPAT]) could serve as a substitute for PASI and would have much interest for physicians in the treatment of psoriasis patients. Preliminary work in regression modeling has shown that a two-factor model utilizing the clinical measure of BSA, as well as one health outcome measure (Itch NRS, Skin Pain VAS, or PatGA), predicts PASI very well and predicts DLQI moderately well. As Itch NRS is a regularly collected measure in medical practice, Itch NRS combined with BSA would provide a convenient tool for physicians to use for the assessment of psoriasis severity.

All possible regression model selection will be performed using ordinary least square models for PASI in the following three populations at week 12: (1) ITT population (pooled treatment groups); (2) ITT population treated with ixekizumab; (3) ITT population with guselkumab. For each population, 29 models adjusting for different independent variables will be fitted.

Independent variables in each model will include individual or combinations of BSA, one of the patient reported assessment variables (Itch NRS, Skin Pain VAS, PatGA), interaction between BSA and patient reported outcome variables, as well as the higher order polynomials/interactions of BSA and patient reported outcome variables (Itch NRS, Skin Pain VAS, PatGA). 20 repeated 10-fold cross-validation (CV) will be used to assess the performance of each model. For each 10-fold CV, 9 out of 10 subsets will be used for model development (training data) and the remaining one subset will be used for validation (test data). Measures including R-squared, adjusted R-squared, Akaike information criterion (AIC), Bayesian information criterion (BIC), mean error (ME), mean absolute error (MAE), mean squared error (MSE), predicted residual error sum of squares (PRESS) will be reported for the 29 models and the testing data based on repeated 10-fold CV in order to select the best performing model. Estimated values from model(s) with high prediction power for PASI based on R-squared will be compiled.

Assessments will be done to evaluate the gain in R-squared from adding in factors into the models.

Using the information from the modeling described above, while keeping with the main objective of a simpler alternative for PASI, two-factor regression models for PASI and for DLQI will be assessed using the same predictors, i.e., BSA and each of the patient outcome measures (Itch NRS, Skin Pain VAS, or PatGA) with the primary focus on Itch NRS, in order to see if the results show good prediction of PASI. The primary timepoint will be week 12 although baseline, Week 4, and Week 8 will also be considered. The models will be assessed with pooled data of both ixekizumab and guselkumab treatment groups, as well as data from each treatment group individually. Graphs will be provided for residuals and for the predicted vs actual PASI values for the Week 12 models. In addition, for each of the models at Week 12, the concordance of the 50/75/90/100 percentage improvement in predicted PASI with observed PASI50/75/90/100 will

be summarized. For Week 12, Youden's Index will be calculated for each of the models, and the sensitivity/specificity /NPV/PPV will be provided as well as the McNemar's Test and Gamma Statistic for the predicted PASI improvement versus the observed PASI50/75/90/100.

The information from both the all possible regression modeling and the delve into the simpler, two-predictor models will be evaluated in order to determine the subsequent results to be incorporated into an interactive tool. Physician will then be able to utilize this simple tool in the office setting while evaluating their psoriasis patients.

The above analyses will be conducted based on the combined treatment group at the interim database lock to keep the integrity of Blinded Treatment Periods. The analyses based on both combined and by treatment group analyses will be conducted after the final database lock.

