6.1.2. Baseline Definition

For the Blinded Treatment Periods, the baseline value will be defined as the last available value before the first treatment injection for both efficacy/health outcomes and safety analyses. In most cases, this will be the measure recorded at Week 0 (Visit 2). For efficacy/health outcome measures, if the patient does not take any injection, the last available value on or prior to randomization date will be used.

Change from baseline will be calculated as the postbaseline value minus the baseline value. Percent change from baseline is defined as: 100 times the change from baseline divided by baseline). Percent improvement from baseline is calculated as: the positive percent change from baseline if a higher value postbaseline means improvement from baseline; and as the negative percent change from baseline if a lower value postbaseline means improvement from baseline. If the baseline value is missing for a particular variable, then the change from baseline and the percent improvement from baseline will not be calculated.

For safety analyses using a baseline period, the baseline period is defined as the time from Visit 1 to the date/time of the first injection.

For the Post-Treatment Follow-Up Period, the baseline is defined as the last nonmissing assessment on or prior to entering Period 4, that is, on or prior to Week 24 (Visit 12), or at the early termination visit (ETV).

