		PASI change from baseline	Calculated as: observed PASI – baseline PASI.	Missing if baseline or observed value is missing
		PASI percent improvement from baseline	Calculated as: $Percent\ improvement\ from\ baseline = 100 \times \frac{Baseline\ PASI - Observed\ PASI}{Baseline\ PASI}$ If a patient has experienced an improvement,	Missing if baseline or observed value is missing

Measure	Description	Variable	Derivation/Comment	Processing of Missing Components
	
6 = 90% to 100%
 
The various body regions are weighted to reflect their respective proportion of body surface area.
		this measure will be positive. If a patient has experienced a worsening in the condition, this measure will be negative.	
		PASI 50	A clinically meaningful response; at least a 50% improvement in PASI score from baseline.	Missing if baseline or observed value is missing.
		PASI 75	A clinically meaningful response; at least a 75% improvement in PASI score from baseline.	Missing if baseline or observed value is missing.
		PASI 90	Higher level of clearance; at least a 90% improvement in PASI score from baseline.	Missing if baseline or observed value is missing.
		PASI 100 (Primary)	Complete resolution of plaque psoriasis; a 100% improvement in PASI score from baseline.	Missing if baseline or observed value is missing.
		PASI ≤1	A PASI ≤1.	Missing if PASI is missing.
		PASI ≤3	A PASI ≤3.	Missing if PASI is missing.
		PASI ≤5	A PASI ≤5.	Missing if PASI is missing.
		Time to first PASI 50; Time to first PASI 75; Time to first PASI 90; Time to first PASI 100	Calculated as: (Date of first PASI 50 response in defined treatment period – Date of first dose + 1) / 7. If the date of first dose is missing, the date of randomization is used. Similarly for PASI 75, PASI 90, and PASI 100.	
sPGA	sPGA is the physician’s global assessment of the patient’s psoriasis lesions at a given time point (EMA 2004 [WWW]). Plaques are assessed for induration, erythema, and scaling, and an overall rating of psoriasis severity is	sPGA score	Range from 0 to 5: clear (0), minimal (1), mild (2), moderate (3), severe (4), or very severe (5).	Single item, missing if missing.
		sPGA (0,1)	An sPGA assessed as either 0 or 1, which represents a clinically meaningful response of minimal plaque severity or complete	Missing if sPGA is missing.

Measure	Description	Variable	Derivation/Comment	Processing of Missing Components

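### In the exploratory OPAT validation, predicted PASI 100 requires an unconstrained least-squares prediction of zero or below, so the PASI 100 accuracy row says little about whether the tool detects clear skin

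*SAP*

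**What the plan says.** SAP Section 6.12.1, which is labelled exploratory, aims at a simple stand-in for PASI for use in the clinic. "All possible regression model selection will be performed using ordinary least square models for PASI" at Week 12, with 29 candidate models per population. The predictors are BSA, one patient-reported score, their interaction, "as well as the higher order polynomials/interactions of BSA and patient reported outcome variables". A second stage narrows to two-factor models with "BSA and each of the patient outcome measures (Itch NRS, Skin Pain VAS, or PatGA) with the primary focus on Itch NRS".

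For Week 12 the section then asks for "the concordance of the 50/75/90/100 percentage improvement in predicted PASI with observed PASI50/75/90/100". Youden's "Index will be calculated for each of the models, and the sensitivity/specificity /NPV/PPV will be provided", together with McNemar's test and gamma.

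Table RHCR 6.4 defines observed PASI 100 as "Complete resolution of plaque psoriasis; a 100% improvement in PASI score from baseline". Section 6.1.2 computes percent improvement as "the negative percent change from baseline if a lower value postbaseline means improvement from baseline", which is the case for PASI.

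The section does not set a floor at zero, a rounding rule or tolerance for the prediction, or a separate cut-off for predicted PASI 100. It does not say whether the baseline used for predicted improvement is observed or predicted. It mentions preliminary modelling but gives no coefficients.

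**The concern.** Observed PASI reaches zero exactly in a clear patient. A least-squares prediction is not bounded at zero and will almost never equal it; whether it falls just above or just below for a clear patient is an accident of fit. Using the same 100% threshold for both therefore asks whether the fitted surface dips to zero near the origin. It does not ask whether the predictors separate clear from non-clear skin.

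At stake is the PASI 100 row of the concordance table: sensitivity, specificity, PPV, NPV, Youden, McNemar and gamma. The results of Section 6.12.1 inform what goes into an interactive tool for physicians. That row could suggest that the tool cannot recognise clear skin, although a BSA of 0 should identify it almost directly.

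**Working it through.** The plan states no figure for this analysis, so there is none to reproduce. The algebra below is exact; every simulated value is illustrative.

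**1. What the threshold requires.** With baseline B and prediction P, percent improvement is 100 × (B − P)/B. For B > 0, this is at least 100 if and only if P ≤ 0. Observed baseline PASI is at least 12 under inclusion criterion [3] of the protocol. The result is the same for any positive predicted baseline.

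**2. What a clear patient is predicted.** At BSA = 0 and itch = 0, every listed form (linear, interaction, polynomial) predicts the intercept a, assuming the usual model with an intercept. All predictors are zero or above. If the slopes are also non-negative, a > 0 implies P > 0 for everyone: no predicted PASI 100, sensitivity 0, specificity 1, Youden 0 + 1 − 1 = 0, PPV 0/0.

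**3. How sharply the row moves.** Assumptions: n = 960 (SAP Section 5.3), slopes of 0.45 per 1% BSA and 0.15 per itch point, about 60% of clear patients with itch 0, and a target clear share of (35.3% + 23.0%)/2 = 29.15%. The simulated data set had 272 clear patients.

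| Intercept | Classed PASI 100 | Sensitivity | Specificity | PPV | Youden |
|---|---|---|---|---|---|
| +0.1 | 0 | 0 | 1 | undefined | 0 |
| +0.01 | 0 | 0 | 1 | undefined | 0 |
| −0.01 | 169 | 0.621 | 1.000 | 1.000 | 0.621 |
| −0.1 | 178 | 0.621 | 0.987 | 0.949 | 0.608 |
| −1 | 475 | 1.000 | 0.705 | 0.573 | 0.705 |

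At −0.01, a clear patient with itch 1 is predicted −0.01 + 0.15 = 0.14, so only clear patients with itch 0 are caught: 169/272 = 0.621. At −1, a patient with itch 0 is classed as clear up to a BSA of 1/0.45 = 2.2%, and PPV falls to 272/475 = 0.573. With BSA alone, moving the intercept from +0.01 to −0.01 moves Youden from 0 to 1.

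**4. Which sign is likely.** Table RHCR 6.4 gives area grade 1 to any regional involvement above 0% and below 10%. Slight redness, thickness and scaling on the lower limbs alone score 0.4 × (1 + 1 + 1) × 1 = 1.2, however small the area. PASI therefore rises steeply just above BSA = 0, which tends to lift a low-order fit at the origin.

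Two separate simulations used these grades and weights, with 23% to 40% clear, three assumed levels of residual disease, three BSA plus itch model forms and 200 trials per cell. In both, the intercept was positive in every run (smallest 0.02 and 0.08), and PASI 100 sensitivity was 0 in all 27 cells. R-squared was 0.41 to 0.85 in one and 0.44 to 0.77 in the other. In a third set, the BSA plus itch intercept was about 0.9 to 1.0 and PASI 100 sensitivity was 0, while PASI 90 Youden was 0.77 to 0.81. The zero thus came from the cut-off and did not reflect a poor model.

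**5. Other shapes.** Under linear or convex BSA–PASI shapes, either sign occurred. In one linear-shape data set the BSA plus itch model had intercept −0.022, R-squared 0.877 and Youden 0.982. On the same data the quadratic model had intercept +0.044, a higher R-squared (0.889) and Youden 0.

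**6. The lower thresholds.** At the minimum baseline of 12, PASI 90 needs P ≤ 1.2, PASI 75 needs P ≤ 3.0 and PASI 50 needs P ≤ 6.0. A clear patient predicted 1.0 shows 100 × (12 − 1)/12 = 91.7% improvement and counts as PASI 90. These thresholds lie above zero and do not have the boundary problem.

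**The case against.** Three stronger readings are tempting, and the documents support none of them.

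- **The sign of the intercept alone sets the statistics.** It does not. Once the intercept is negative, its size relative to the slopes and the spread of itch scores matter, as the table shows. With an itch slope of −0.15 and an intercept of +0.1, sensitivity was 0.38. Interactions and polynomials also allow a positive intercept to coexist with predictions below zero.
- **The intercept will be positive, so the row will certainly show zero sensitivity.** The area grades make this likely for BSA plus itch but do not prove it, and no OPAT coefficients are given. PatGA, anchored at 0 for clear, may behave differently. Under some assumed noise, BSA plus PatGA intercepts averaged 0.01 to 0.18 with some negative runs, and one interaction scenario had mean sensitivity 0.39. Under other assumptions, sensitivity stayed essentially 0. Some cubic itch fits also had negative intercepts.
- **The trial's primary endpoint is compromised because it is PASI 100.** The primary test is a CMH test on observed PASI with nonresponder imputation (SAP Section 6.11.1). OPAT is not in the testing sequence of Section 6.4.

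It can also be said that observed PASI moves in steps of 0.1, so predictions might be rounded. The SAP does not say so, and the effect is erratic. Rounding left sensitivity at 0 in the area-grade BSA plus itch simulation where it was tried. It raised one linear-shape fit (intercept 0.048) from 0 to 0.62, and gave 0 to 0.85 across PatGA runs.

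Finally, the consequences are limited. Model selection rests on R-squared, information criteria and cross-validated error. Residual and predicted-versus-actual plots are planned, and all the evidence is weighed before the tool is built. A row with no predicted responders would be seen. This stands, and it lowers the weight of the point. It does not make the row informative.

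**Conclusion.** The literal rule classes a patient as predicted PASI 100 only when an unconstrained least-squares prediction is zero or below. For BSA alone, or with non-negative slopes, a positive intercept leaves nobody in that class. A negligible shift to the other side of zero changes Youden from 0 to 0.62 with BSA and itch, or from 0 to 1 with BSA alone. A statistic that moves this much on a difference of 0.02 PASI points does not measure how well the tool detects clear skin, whichever sign occurs.

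The algebra needs only a positive baseline; the statement about clear patients also assumes a fitted intercept. The accuracy values and the likelihood of a positive intercept rest on assumed BSA, itch and PatGA distributions. The point is minor: it affects one of four rows in an exploratory table. It touches no treatment comparison, error rate or sample size.

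**What to change.** In SAP Section 6.12.1, for the PASI 100 row only:

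- Replace the literal 100% threshold with a cut-off on predicted PASI. Choose it in the training folds (for example, by maximum Youden) and score it in the test folds of the planned 10-fold cross-validation, repeated 20 times. If all predictions shift by a constant, such a cut-off shifts with them and the classification is unchanged, so the dependence on the intercept disappears.
- Report BSA = 0 as a simple reference rule, to show what the model adds.
- State whether predictions are rounded before classification.
- Keep the fixed 50/75/90 thresholds.

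A logistic model for PASI 100 on the same predictors is a reasonable option but not necessary, and it departs from the aim of a single simple substitute for PASI.

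Cost: SAP wording, a few lines of programming and one extra parameter in the tool. No new data are needed.
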